Hypothesis: Baclofen will modulate resting brain activity—specifically, activity in the lateral orbitofrontal cortex, involved in aversive processing, will be greater in baclofen-treated subjects. Baclofen will modulate smoking cue reactivity: activity in reward-related regions will be blunted in subjects receiving baclofen, while those receiving placebo will display the original signature of craving observed in our well-characterized smoking cue reactivity paradigm. Baclofen will correct vulnerabilities by modulating neural activity in the amygdala and ventral striatum, regions known to respond to reward and in the insula, which is considered an autonomic signaling relay station and plays a role in drug craving. Although overall effects are expected, inter-individual variability in pharmacological response introduced by genetic variance in the DAT will be evidenced.

AIM 3. In a 2 x 2 design (DAT genotype) x (baclofen versus placebo), examine the interaction between allelic variance in the DAT and baclofen-induced neuromodulatory and behavioral responses.

Hypothesis: DAT genotype will underlie the inter-individual variability in brain and behavioral responses to baclofen. 9-repeats receiving baclofen will demonstrate greater reductions in reward-related brain activity and smoking behavior compared to 10/10 repeats.

Optional Sub-Study Aim: Conduct an optional sub-study to examine the effects of baclofen on brain responses to alcohol cues (compared to non-alcohol cues) and drinking behavior compared to placebo following 4 weeks of baclofen or placebo in individuals actively seeking smoking cessation treatment and drink heavily. The goals, rationale, background and study methods for this objective are described in Appendix I.

2. Primary Outcome Variable(s)

Brain and behavioral responses to smoking cues will be significantly greater in 9-repeats compared to 10/10-repeats. Although overall effects are expected, inter-individual variability in brain response introduced by genetic variance in the DAT will be evidenced. 9-repeats receiving baclofen will demonstrate greater reductions in brain activity and smoking behavior compared to 10/10-repeats.

3. Secondary Outcome Variable(s)

Pre-medication outcome variables:

9-repeats may have more difficulty labeling their feelings as measured by higher scores on the Toronto Alexithymia Scale (TAS).

9-repeats may have higher attention deficit (ADHD) symptoms as measured by the ADHD battery.

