Non-abstinent subjects will be randomized by sex and DAT genotype. We will use our perfusion fMRI/cue paradigm to acquire resting baseline (RB) and SC data to confirm and extend our finding of a DAT-mediated SC-vulnerable endophenotype; 9-repeat carriers will exhibit enhanced brain activity in the interconnected VS/mOFC (regions involved in conditioned drug reward) compared to 10/10-repeats. Behavioral responses, including craving and cigarette consumption, will be significantly greater in 9-repeat carriers compared to 10/10-repeats following SC exposure.

Within the 2 x 2 design (9-repeat carriers vs 10/10-repeats) X (baclofen vs placebo), treatment-seeking subjects will participate in an 8-week medication regimen. Baclofen or placebo will be prescribed to non-abstinent subjects at the same doses that have been demonstrated to be clinically effective in our Smoking Reduction Trial. The importance of subjects being non-abstinent is twofold. First, our goal is to determine if and how baclofen affects SC reactivity independent of WD to disentangle these two major motivators underlying relapse. Second, differences in smoking behavior modulate brain activity, so it is important that baclofen- and placebo-treated groups have similar smoking characteristics.

3. Study Duration

This study requires a one-week screening phase and 8 weeks of monitoring and medication. All subjects will complete 2 MRI sessions (one before starting medication, one following 3 weeks of medication) and 5 weeks of additional treatment. Each subject will be enrolled in the study for approximately 10 weeks.

The entire study will commence 12/01/2012 and will run until 08/31/2017, approximately. 20 to 25 subjects will be randomized each year.

DRUGS OR DEVICES

Baclofen and matching placebo

STUDY PROCEDURES

General Procedures

*Interested potential subjects will be screened with a structured interview. Individuals who may qualify are scheduled for the consenting visit. If the consent is successful, individuals will be scheduled to come in for physical and psychological examinations and to provide a genetics sample.

*After the results of the examinations are reviewed, the subject will be contacted to inform them whether or not they qualify. If the examinations reveal any health problems that require medical attention, the subject will be referred to their family physician.

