*Part of the physical ** Part of the Psych Eval *** Collected pre- and post scan ⁺ Occurs the same day as the Quit Wk appt

2. Analyses

Imaging Data Processing: Prior to performing analyses, brain data are examined for gross movement and full image acquisition. An SPM-based ASL data processing toolbox is used for data analyses. ASL image pairs are realigned to the mean of all control images and spatially smoothed with a 3D isotropic Gaussian kernel with FWHM of 10mm. CBF image series are generated using a simplified two-compartment model with the sinc interpolation method for CBF calculations. The mean control image of each subject's data is co-registered to a HR 3D T1 structural image using the mutual information based co-registration algorithm provided by SPM8. The same co-registration parameters are used to co-register the CBF maps to the structural image. The structural image is then spatially normalized to the MNI standard brain. The same parameters are used to normalize the CBF images to the MNI standard space. Each subject's normalized mean control images are segmented using SPM8. The segmented gray matter masks are averaged and the overlap of subject's gray matter is extracted. This final mask is used for calculating global CBF for each session.

Imaging Data Analyses: Voxel-wise analyses of the CBF data are conducted on each subject using a general linear model (GLM). Global CBF time course is included in the model as a covariate to examine the effects of baclofen. Analyses are conducted on absolute (RB) and relative (during SC exposure) CBF. No temporal smoothing is applied. Contrasts between conditions (Time 1 versus Time 2) are defined in the GLM model to assess the voxel by voxel CBF difference. Using the corresponding parametric maps of this contrast (maps), random effects analysis is employed to test for a significant main effect of condition with a SPM map of the T statistic at each voxel for population inference for each session for the placebo and baclofen groups (second-level analysis). A 2x2 factorial design matrix is used to assess the effects of the pharmacological manipulation by including the group (baclofen vs placebo) and condition (Time 1 vs Time 2) as the two factors. This two-stage analysis is theoretically equivalent to a 2 way ANOVA.

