We have recently gained expertise in connectivity analysis, which we will utilize here as in our previous studies. This approach determines the degree to which the time course of each voxel correlates with the averaged time course from a specific region of interest (e.g., the VS/mOFC). In this approach, the time course of all voxels within this region of interest will be extracted, and the averaged time course will be used as the regressor to check the correlation between the seed region and the rest of brain. As an alternative, we can repeat the same correlation analysis but using the principal component of all time courses extracted from the ROI as the reference function. For each subject, the β map of the voxel wise connectivity analysis (correlation analysis) will be collected, and group analysis through random effects using one-sample t-tests will be performed to assess the across-subject effects of the brain connectivity to the seed region of interest. Neuropsychological and behavioral scores can be used as simple regressors to examine their relationship to connectivity for a brain target. Though our focus for the project is VS/mOFC connectivity due to its role in emotional arousal, the same analyses can be performed for other regions of interest (e.g., lateral OFC).

Behavioral Analyses: Statistical significance tests use an alpha of .05 unless otherwise noted. Continuous demographic variables (e.g., age, education, FTND, CPD, pack years, TAS, RSQ, SJ, mCEQ and the CWQ composite scores, latency to smoke, and cigarette consumption) are checked for normality, transformed if necessary, and summarized by calculating means, standard deviations and ranges. Scores on each factor will be included as covariates of interest with respect to perfusion fMRI SC data and genetic variance in DA-ergic components. Analysis of variance will be used to assess demographic differences across groups. Nominal demographic variables (e.g., race, sex, genotype) are summarized by calculating proportions and compared across groups using chi square analyses. Demographic (age, years education, monthly income) and clinical (depression, anxiety and psychiatric symptom scores) will also be summarized and compared across the treatment groups.

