Genetics Analysis: Genomic DNA will be extracted from anticoagulated venous blood samples using a standard salting out method. Genotyping of the DRD4 and DAT VNTR will be performed using standard methods as described previously. DRD2 and COMT genotypes will be determined using the Applied Biosystems Inc. (ABI) Assays-on-demand (ABI, Foster City, CA, USA) SNP genotyping assay as per manufacturers protocol. Genotyping quality control steps for all markers will include Hardy-Weinberg equilibrium determination and genotyping of 20% duplicates for each marker.

Solanesol Assay: Cigarette filters from cigarettes smoked at specific study time points will be collected and stored for future analysis.

Sample Size Determination and Power: Using our published findings examining the effects of the DAT polymorphism on SC reactivity, we calculated an effect size of 0.78 in the VS and 0.98 in the OFC. These effect sizes will allow us to determine between group differences at greater than 0.80 power with group sizes ranging from 18-24. Importantly, in other studies ongoing in our lab, none of the genotypes examined deviated from those expected from Hardy Weinberg Equilibrium. The proposed number of subjects should be adequate to acquire data on the effects of the several brain, behavioral and genetic endpoints. We are also encouraged that we will find between group differences by results of studies that have utilized similar sample sizes. With these sample sizes it should be possible to generate groups large enough to explore gene-gene interactions. Smolka et al was one of the first studies to demonstrate that functional brain imaging can be used to assess the interaction of multiple genes on the function of neuronal networks. They observed an additive effect of COMT and 5-HTT polymorphisms (N=48), accounting for 40% of the inter-individual variance in the averaged BOLD response of amygdala, hippocampal and limbic cortical regions elicited by unpleasant stimuli. We will examine the interaction between COMT and DAT genotypes first as we have preliminary data suggesting a gene-gene interaction on cue reactivity (not presented here). We expect that we will have 15-20 subjects per group (9-repeat carriers / Val carriers, 9-repeat carriers / Met homozygotes, 10/10-repeats Val carriers, 10/10-repeats / Val carriers. Groups will not be large enough to examine the contribution of more than one gene on medication response.

3. Confidentiality

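### Aim 3 asks for a drug by DAT genotype interaction, but the only treatment model in Analyses is drug by time, with neither genotype nor sex in it

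*Combined protocol and SAP*

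**What the plan says.** Aim 3 under Overall Objectives reads: "In a 2 x 2 design (DAT genotype) x (baclofen versus placebo), examine the interaction between allelic variance in the DAT". The Design section sets the trial up to match. It states that "Non-abstinent subjects will be randomized by sex and DAT genotype" and places treatment "Within the 2 x 2 design (9-repeat carriers vs 10/10-repeats) X (baclofen vs placebo"). The Primary Outcome Variable(s) paragraph adds that "9-repeats receiving baclofen will demonstrate greater reductions in brain activity and smoking behavior compared to 10/10-repeats".

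Under Imaging Data Analyses, the treatment model is a different 2x2, built "by including the group (baclofen vs placebo) and condition (Time 1 vs Time 2) as the two factors", and the text calls it equivalent to a two-way ANOVA. The one covariate named there is global CBF.

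Genotype comes up elsewhere in Analyses, but never crossed with drug:

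- The connectivity analysis uses one-sample t-tests.
- Behavioral Analyses enters behavioral scores as covariates in relation to cue data and dopaminergic genetic variance.
- The same section says "Nominal demographic variables (e.g., race, sex, genotype) are summarized by calculating proportions and compared across groups using chi square analyses".
- Sample Size Determination and Power plans a COMT by DAT analysis of cue reactivity and remarks that "Groups will not be large enough to examine the contribution of more than one gene on medication response". This implies that one gene and medication response will be examined, but gives no model.
- The power statement, based on DAT effects of 0.78 (VS) and 0.98 (OFC), is: "These effect sizes will allow us to determine between group differences at greater than 0.80 power with group sizes ranging from 18-24".

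**The concern.** A drug by time model averages the drug effect over genotype. Followed exactly, it returns no estimate, test or interval for the question that Aim 3 asks. The trial stratifies on genotype to support that question and then leaves genotype out of the model.

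Three things are left open: the form of the model, which imaging and smoking measures carry the test, and the time point. The last matters because cotinine is measured at both scan days and at Week 8, and the quit attempt falls between the second scan and Week 8.

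The Primary Outcome sentence adds a smaller uncertainty. It speaks of carriers on baclofen compared with 10/10 subjects. Read literally, that could be a genotype comparison inside the baclofen arm, which is a different quantity from the interaction.

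The only power figure in the plan concerns two-group differences, so a reader could wrongly take it to cover Aim 3. The absence of sex, the other randomization factor, is a lesser point.

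**Working it through.** **1. Can the stated model give the Aim 3 contrast?** Write the mean Time 2 minus Time 1 change as b9 and b10 (baclofen; carriers and 10/10) and p9 and p10 (placebo).

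- Drug by time model: estimates (pooled baclofen change) - (pooled placebo change). Genotype does not appear.
- Aim 3: (b9 - p9) - (b10 - p10). This needs a drug by genotype term on the change, or equivalently drug by genotype by time.
- Comparison within the baclofen arm: b9 - b10. It equals the Aim 3 contrast only if p9 = p10.

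No sentence in Analyses adds the missing term.

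**2. The plan's own power figure.** For two equal groups, two-sided alpha 0.05 and 80% power, n per group = 2(1.960 + 0.842)²/d². This gives 25.8, so 26, for d = 0.78 and 16.3, so 17, for d = 0.98. The plan says 18-24. Exact t power is 0.75 at 24 per group with 0.78, and 0.82 at 18 per group with 0.98. Sidedness is not stated; one-sided, the first figure is 0.85. The calculation is therefore recognisable as a two-group comparison and does not address an interaction.

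**3. Precision ratio.** Let n9 and n10 be the genotype totals, with 2:1 allocation (Randomization) inside each and a common SD.

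- Two-group genotype variance: 1/n9 + 1/n10.
- Interaction variance, the sum of 1/n over four cells: (1/n9 + 1/n10) × [1/(2/3) + 1/(1/3)] = (1/n9 + 1/n10) × 4.5.
- SE ratio: sqrt(4.5) = 2.12, whatever the genotype split.

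**4. Genotype split.** The sample size text expects 15-20 subjects in each of four DAT by COMT groups, two of carriers and two of 10/10. One COMT label is repeated, but the DAT labels are clear. That is 30-40 per DAT genotype, so the carrier share runs from 30/70 = 43% to 40/70 = 57%.

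**5. Interval width.** Completers: 100 - 15 = 85 (Accrual). Residual df with drug, genotype, interaction and sex: 85 - 5 = 80, and t(0.975, 80) = 1.990.

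| Carrier share | Cells | Interaction SE | Two-group SE | 95% half-width |
|---|---|---|---|---|
| 50% | 28.3 / 14.2 / 28.3 / 14.2 | 0.460 | 0.217 | 0.92 |
| 43% or 57% | 24.3 / 12.1 / 32.4 / 16.2 | 0.465 | 0.219 | 0.93 |

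Units are SD of the analysed variable.

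**6. Illustrative power.** The documents give no interaction size. Borrowing 0.78 and 0.98, with the noncentral t on 80 df:

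- In SD of change: 0.38-0.39 at 0.78 and 0.55-0.56 at 0.98.
- In single-scan SD, the size is divided by sqrt(2(1 - r)), with the scan-rescan correlation r assumed to be 0.3-0.7. The lowest case is 0.78/1.183 = 0.66, power 0.29. The highest is 0.98/0.775 = 1.27, power 0.78.

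**7. What the drug coefficient means.** Once drug by genotype is in the model, a reference-coded drug coefficient is the effect in one genotype only. At 50:50 its SE is sqrt(1/28.3 + 1/14.2) = 0.325. The drug effect averaged over genotype has SE sqrt(1/56.7 + 1/28.3) = 0.230.

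**The case against.** The fairest defence is that much of Aim 3 is already fixed. The Objectives and Design name the two factors, their levels, the word interaction and the expected direction, and Background and Design point to the VS/mOFC. Genotype is also more than a descriptive variable in Analyses, given the covariate sentence and the COMT by DAT plan. This stands. A reader might infer that the Aim 3 analysis was never intended, or that it would be chosen freely once the data are seen. The documents do not support either reading. What is missing is the model, the outcome and the window.

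A reader might also infer that the Primary Outcome sentence commits the trial to a comparison inside the baclofen arm. Nearly the same sentence is the hypothesis printed directly under Aim 3, so the interaction is the more natural meaning. The sentence should still say so, because the comparison inside one arm would also pick up any genotype difference in change that occurs on placebo.

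It is also true that 0.78 and 0.98 are genotype effects on cue reactivity, not interaction sizes, so the power figures are illustrations.

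**Conclusion.** The point holds and should be fixed before analysis: a stated aim, and most naturally part of the primary outcome, has no model in the plan that can answer it. This conclusion rests on the text alone.

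The 2.12 ratio needs only 2:1 allocation within each genotype and a common SD. The half-width of 0.92-0.93 SD also needs 85 completers and the implied 43-57% carriers. Illustrative power is 0.38-0.56 in SD of change, or 0.29-0.78 in single-scan SD with correlation 0.3-0.7.

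A reader might go on to conclude that the trial is shown to be underpowered for Aim 3. The documents do not allow that, since they give neither an interaction size nor a scan-rescan correlation. They show only that the stated power does not apply to it. Nor does the point fault drug by time as a model for Aim 2.

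**What to change.** 1. At second level, analyse one Time 2 minus Time 1 map or regional mean per subject, with terms for drug, DAT genotype, drug by genotype and sex.
2. Test Aim 2 as the drug effect averaged over genotype, with the weights stated (for example through centred or effect coding), not as a reference-coded drug coefficient.
3. Test Aim 3 as drug by genotype. Name one primary Aim 3 imaging test; cue CBF in the VS/mOFC is the natural candidate, because the plan's drug and genotype hypotheses meet there.
4. Use the same terms for change in cigarettes per day and urine cotinine, at a stated time point.
5. State that the Primary Outcome sentence means this interaction.
6. State that the power figure covers two-group differences only and does not apply to Aim 3. Report the interaction estimate with its confidence interval.

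The cost is wording plus three between-subject degrees of freedom: with 85 completers, residual df falls from 83 (drug only, on change scores) to 80. No new data are needed. The price is a less favourable power statement for Aim 3.

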Our approach capitalizes on the neuroimaging technique of pseudo-continuous arterial spin labeled (PCASL) perfusion fMRI. Perfusion fMRI is a non-invasive, non-radioactive technique that is used to measure neurophysiological activity. It uses magnetic field to induce a radio-frequency signal to reflect the brain anatomy and the changes in CBF in near real-time. Changes in CBF result in changes in tissue contrast, measured reliably with MRI scanners. Perfusion refers to the delivery of oxygen and nutrients to tissue by means of blood flow and is regionally coupled to brain metabolism. Perfusion fMRI is distinguished from BOLD contrast, which is acquired via oxygenated vs. deoxygenated hemoglobin. **Perfusion fMRI is quantitative (94) and stable across time (95), which facilitates the measurement of brain responses at various time points, both in response to cognitive and emotional tasks, such as cue exposure (76, 83), and also in the brain in the resting condition (without provocation) (96, 97).** As such, perfusion fMRI is ideal for longitudinal studies examining brain modifications induced by pharmacological agents. BOLD fMRI is a relative measure, which can only accurately examine changes that occur within a scanning session, during a task, or other provocation and cannot reveal changes induced by a chronic (or otherwise) treatment. Another feature of perfusion fMRI is that noise characteristics are stable over the entire frequency spectrum, which makes it suitable for studying low-frequency events in brain function, such as craving and other emotional states that

accrue over time (83, 94, 98, 99). Consequently, in our paradigm, this stable and quantitative technique has distinct advantages over BOLD imaging for revealing the neurobiological mechanisms underlying task performance (i.e., cue exposure) and its modulation by pharmacological agents.

Other factors involved in smoking behavior:

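### The baclofen imaging model names only group and time, with no subject, repeated-measures or baseline term for paired scans; fitted as written, the drug x time test is conservative and underpowered

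*Combined protocol and SAP*

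**What the plan says.** Under Study Design, Study Duration: "All subjects will complete 2 MRI sessions (one before starting medication, one following 3 weeks of medication". The data for Aim 2 (baclofen versus placebo) are therefore paired within subject.

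The section Imaging Data Analyses then describes these steps:

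- A first stage for each person: "Voxel-wise analyses of the CBF data are conducted on each subject using a general linear model (GLM".
- A time contrast in that first stage: "Contrasts between conditions (Time 1 versus Time 2) are defined in the GLM model to assess the voxel by voxel CBF difference".
- A second stage on the resulting contrast maps, for the placebo and baclofen groups: "random effects analysis is employed to test for a significant main effect of condition".
- A two-by-two factorial matrix for the drug effect, "including the group (baclofen vs placebo) and condition (Time 1 vs Time 2) as the two factors".
- A closing statement: "This two-stage analysis is theoretically equivalent to a 2 way ANOVA".

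The section names no subject factor, repeated-measures error term, covariance structure or Time 1 covariate. It does not say whether the two-by-two matrix takes difference maps or separate session maps, nor which contrast (drug x time, or group averaged over time) is the test of baclofen.

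The background section on the perfusion paradigm supports repeat scanning on the ground that "Perfusion fMRI is quantitative (94) and stable across time (95" (the numbers are its references). It gives no scan-rescan correlation.

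**The concern.** A two-way ANOVA with group and time as its only terms has a single error variance that mixes between-subject and within-subject variation. If a subject's two scans are positively correlated, that pooled error is too large for the change comparison. The comparison then loses the precision that scanning each person twice was meant to provide.

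This is the only between-arm imaging model written out in the analysis section. The connectivity analysis is described with one-sample tests, and Aim 3 adds genotype but has no imaging model spelled out. Which between-arm contrast is tested, and with which error term, therefore decides how Aim 2 is answered. The short results text at the end of the document shows why this needs to be explicit: it describes a reduction on baclofen and none on placebo, and its text gives no between-arm statistic.

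**Working it through.** **No stated figure to reproduce for this test.** The only power statement (Sample Size Determination and Power) concerns the DAT genotype contrast: effect sizes 0.78 and 0.98, with 18 to 24 per group. The two-sided normal formula gives 26 and 17 per group for those effect sizes, close to the stated range, but this does not bear on baclofen.

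**Do the sentences fit together?** A Time 2 minus Time 1 map gives one image per subject, and time has already been used up in forming it. A second-level matrix with time as a factor needs two images per subject. The two-by-two sentence, taken literally, therefore needs separate session maps. With only group and time in the model, nothing then links the two maps of one subject.

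**Inputs**

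- 100 randomized, 15 expected lost (Accrual): 100 - 15 = 85.
- 2:1 baclofen to placebo (Randomization): 85 x 2/3 = 56.7, so 57 v 28.
- Alpha 0.05: "Statistical significance tests use an alpha of .05 unless otherwise noted", which stands under Behavioral Analyses. Two-sided is assumed. No voxel-wise threshold is given.
- Assumed: r from 0 to 0.7, equal variances (SD 1), and an arm difference in change of 0.5 SD.

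**Formulas**, with h = 1/57 + 1/28 = 0.0533:

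- Drug x time SE if the scans are entered as independent: sqrt(2h) = 0.326, whatever r is.
- True SE of the arm difference in change: sqrt(2(1-r)h). The ratio of the two is 1/sqrt(1-r).
- SE for Time 2 adjusted for Time 1: sqrt((1-r²)h).
- Power of the independence model: Φ((0.5 - 1.96 x 0.326)/true SE). Power of the other two: Φ(0.5/SE - 1.96).

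Worked at r = 0.5: the true SE is sqrt(2 x 0.5 x 0.0533) = 0.231, and the ratio is 0.326/0.231 = 1.41. Independence model: (0.5 - 0.640)/0.231 = -0.605, power 0.27. Paired change: 0.5/0.231 - 1.96 = 0.207, power 0.58. Baseline-adjusted: SE = sqrt(0.75 x 0.0533) = 0.200, 0.5/0.200 - 1.96 = 0.54, power 0.71.

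| r | SE ratio | actual alpha, drug x time | power as written | power, paired change | power, baseline-adjusted |
|---|---|---|---|---|---|
| 0 | 1.00 | 0.050 | 0.33 | 0.33 | 0.58 |
| 0.3 | 1.20 | 0.019 | 0.30 | 0.45 | 0.62 |
| 0.5 | 1.41 | 0.006 | 0.27 | 0.58 | 0.71 |
| 0.7 | 1.83 | 0.0003 | 0.22 | 0.80 | 0.86 |

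These are normal approximations. Simulation with t-tests at r = 0.3, 0.5 and 0.7 gives 0.30, 0.27 and 0.22 as written, 0.44, 0.57 and 0.79 for paired change, and 0.60, 0.69 and 0.85 with baseline adjustment. A two-sample test on subject differences holds its simulated alpha at 0.049 to 0.051 for every r tried.

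**Group effect averaged over both scans.** The independence SE is sqrt(h/2) = 0.163, and the true SE is sqrt((1+r)h/2), which is 0.200 at r = 0.5. The computed SE is thus 1/sqrt(1+r) of its true size (0.82 at r = 0.5), and actual alpha is about 0.11.

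**The case against.** The strongest reply is that the plan nowhere says the scans are treated as independent. The model is described as two-stage, the first stage is fitted per subject, and it produces a Time 1 versus Time 2 difference. Naming two factors of interest does not by itself fix the error term. If the difference maps feed the comparison of arms, the pairing is respected and the drug x time error is right. This stands as far as intent goes: a reader might infer that the plan states independence, and it does not. Independence is what the two-by-two sentence gives when fitted literally. The reply does not rescue that sentence, because a difference map cannot also carry time as a factor.

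A reader might also infer that the plan's baclofen test has an inflated false-positive rate, from the alpha of about 0.11 for the group effect. The documents do not support that. They never name the group effect averaged over both scans as the baclofen test, and the Aim 2 hypothesis concerns responses blunted on drug. For drug x time, even the literal reading errs on the conservative side.

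The size is open to challenge too. The statement about stability concerns perfusion as a technique, not the smoking-minus-nonsmoking cue contrast, and the effect size and single-outcome alpha are illustrative. This is accepted: the planned test is voxel-wise, so the power values show direction and rough scale only.

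**Conclusion.** The point holds in conditional form. The section is internally inconsistent, and its drug-effect sentence, followed as written, gives the wrong error term whenever r is above 0. The consequence is lost power for Aim 2, not false claims for baclofen. At r = 0.5 the standard error is 1.41 times too wide, and power falls from about 0.58 (paired change) to 0.27. At r = 0 there is no loss from ignoring the pairing, though baseline adjustment would still raise power from 0.33 to 0.58. These figures rest on an assumed r, an assumed 0.5 SD effect, equal variances, 57 v 28 completers and one outcome at two-sided 0.05. The 1/sqrt(1-r) factor does not depend on the sample size or the effect size.

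This is more than missing detail. Even if difference maps were intended, the text needs rewriting, and baseline adjustment would add precision.

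**What to change.** Replace the two-by-two sentence and the ANOVA sentence that follows it with text that does four things:

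1. Names drug x time, meaning the arm difference in change from Time 1 to Time 2, as the Aim 2 imaging test.
2. For the voxel-wise analysis, enters one map per subject and compares baclofen with placebo by a two-sample test on the Time 2 minus Time 1 maps. A model on session maps with a subject term is an acceptable alternative.
3. For the pre-named regions such as VS/mOFC, compares Time 2 values between arms with the same subject's Time 1 value as covariate.
4. States that the group effect averaged over both scans is not used as evidence of a drug effect.

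The cost is one paragraph and a new design matrix on the same scans, with no new data. One small downside is that a Time 1 covariate differs at each voxel and may need an added tool, so baseline adjustment is simplest on region averages.
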